The purpose of this Aim is to evaluate the feasibility of utilizing the 3DIZI technique to optimize BTX injections in patients with focal spasticity. Clinical and quantitative assessments of spastic biceps of stroke subjects between 3DIZI-guided and standard injections at baseline, 3 weeks, and 3 months post-injections will be compared. The clinical effect of BTX injection usually reaches to its peak at about 3 weeks, and lasts for 3 months. It is expected that outcomes (clinical and quantitative measures) will be better in the 3DIZI-guided injection group than in the standard injection group at 3 weeks and 3 months post-injection. Both groups are expected to have comparable baseline measures.

Patient selection: We plan to recruit 16 post-stroke subjects who are currently receiving BTX injections for their spastic biceps every 3 months at TIRR Outpatient Spasticity Management Clinic into two groups: the IZ-guided injection group and the standard injection group (Please see human subject protect section for characteristics of stroke patients).

BTX injections: Both groups of patients will be recruited prior to their routine BTX injection schedule. Baseline assessment (screening, clinical assessment, and quantitative assessment) will be performed 1 day prior to injection. Stroke patients with elbow flexors spasticity of modified Ashworth scale (MAS) of 2 or 3 will be recruited. The number of MAS (2s or 3s) will be matched between two groups. The type of BTX (we will choose botox because it is most commonly used in US) and amount of BTX (usually 100 units) and dilutions (usually double dilution) will be consistent between two groups. These parameters (type, dose, dilution) are standard of care at TIRR Spasticity Management Clinic. For standard injection procedures, target muscles will be visualized under ultrasound imaging which is operated by an experienced and dedicated technician. Position of needle tip within the target muscle is visualized prior to

[figure not shown]

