injection. Ultrasound guidance can help ensure depth of needle tip location, i.e., to make sure the needle tip is within the muscle, but it is not able to tell where it is located with reference to the IZs of the entire muscle. However, in the IZ-guided injection technique, IZ location obtained using the 3DIZ will be first marked over the skin surface of the muscle and the depth of the IZ will be also provided. The 3DIZ as described in Aim 1 will be applied to the IZ-guided injection group 1 day prior to scheduled injection. The surface location and depth information of the IZ will be used to guide where the needle tip needs to go. Currently, patients commonly receive 1 to 2 injection sites, occasionally 3 sites for biceps muscles. To standardize the procedure, we will choose 2 sites for all patients.

Treatment outcome evaluation and comparison: Treatment outcomes include clinical assessment of spasticity (MAS scale, see Human Subject Protection section) and quantitative assessment. Standard physical therapy will be ordered to both groups as part of standard of care for patients after BTX injections to maximize the outcomes. For quantitative assessment, we will adopt the same protocol in our recent study which quantified elbow flexors spasticity by measuring reflex torque (Figure 6)(Bhadane et al. 2015).

Fig. 6: Experimental setting (upper) and representative data (lower).

Each subject will receive a total of 60 degrees of computer-controlled elbow extension stretching at different speeds. The stretch ends at 10 degrees beyond the resting angle of the elbow joint during standing to offset the baseline difference among subjects (Bhadane et al. 2015). From the angle-torque relations, reflex torque is obtained after subtracting passive torque at 5°/sec from those at 50°/sec or 100°/sec. reflex torque is considered to reflect neural component of muscle spasticity (Kamper et al. 2001; Kamper et al. 2003; Li et al. 2006). It is expected to be reduced with spasticity reduction after neuromuscular blockade by Botox.

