These measures will be made at baseline, 3 weeks and 3 months post-injection. Two-way ANOVA with factors of GROUP (x2) and TIME (x3) will be performed on reflex torque values. It is anticipated that MAS scores, reflex torque values are comparable at baseline, but will be significantly reduced at 3 weeks and 3 months for both groups. Reduction is expected to be significantly more in the IZ-guided injection group than in the standard group. We do anticipate great reduction in elbow flexor spasticity as quantified by reflex-torque measurement after the IZ-guided injection. However, MAS scores are not as reliable in general (Craven and Morris 2010), and could be influenced by other elbow flexors.

Pitfalls: If other elbow flexors are required to be injected but may not be consistent across subjects, it is unethical not to inject (treat) these muscles. Assessment of biceps spasticity may be influenced and thus MAS scores may not accurately reflect the spasticity reduction effect from biceps muscles alone. Efforts will be made to balance treatment plans between groups in the recruitment process.

Limitation: Eight patients and 16 patients (8 patients per group) are proposed for Exp 1 and Exp 2 respectively. We expect that 8 subjects in each group should be sufficient to detect difference should it exist, according a recent study (Lapatki et al. 2011). These estimated numbers fit in the scope of work of this 2-year exploratory project. A power analysis will be performed at the completion of this project to decide whether or how many more subjects will be needed for a future study. Full-time biostatisticians are available at both UH and TIRR (see Facilities and Other Resources section) for statistical analysis support.

The implementation of the 3DIZI technique currently proposed in the proposal is relatively complicated, because the main purpose of this project is to evaluate the performance of the proposed 3DIZI and examine the feasibility of its application to clinic. As the next step, we plan to simplify the implementation of the 3DIZI technique to make it appropriate for clinic use.

Specimens:

No specimens will be collected

5. Human Subjects

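### No deciding stretch speed, visit or ANOVA effect is named for the reflex-torque comparison, so a significant group difference cannot be read at its nominal 5% level

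*Combined protocol and SAP*

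**What the plan says.** All references are to the combined protocol and SAP.

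- **Speed.** Section 4, Experiment 2, under treatment outcome evaluation: "reflex torque is obtained after subtracting passive torque at 5°/sec from those at 50°/sec or 100°/sec". This gives two candidate torque values per visit and no rule for choosing or combining them.
- **Outcomes.** The same paragraph: "Treatment outcomes include clinical assessment of spasticity (MAS scale, see Human Subject Protection section) and quantitative assessment". Neither is called primary.
- **Visits.** The opening of Experiment 2 expects that clinical and quantitative outcomes "will be better in the 3DIZI-guided injection group than in the standard injection group at 3 weeks and 3 months post-injection". The two visits are not ranked.
- **Test.** Section 4, repeated in section 6: "Two-way ANOVA with factors of GROUP (x2) and TIME (x3) will be performed on reflex torque values". The text does not say whether GROUP or GROUP x TIME answers the question, and gives no significance level, follow-up contrast or multiplicity rule. No test is named for MAS.
- **Prediction.** "Reduction is expected to be significantly more in the IZ-guided injection group than in the standard group".
- **Standing of MAS.** "MAS scores are not as reliable in general (Craven and Morris 2010), and could be influenced by other elbow flexors".
- **Size and status.** "Eight patients and 16 patients (8 patients per group) are proposed for Exp 1 and Exp 2 respectively". The Limitation paragraph calls the project exploratory, regards 8 per group as enough to detect a difference, and plans a power analysis at completion to size a future study.

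**The concern.** The plan predicts a significant advantage but leaves open which result would show it. The ANOVA can be run on either speed, two of its effects could be taken as the answer, the two visits could be compared separately, and MAS could be brought in. With several correlated results and none named in advance, the most favourable one can become the finding. It would then be quoted at a 5% error rate that does not apply to it.

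The second consequence concerns the future study. Its size is to come from this trial's results, but the plan does not say which result. With 8 per arm, an effect chosen because it was significant is bound to be large.

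**Working it through.** **Inputs from the plan:** 8 patients per group, two speeds, two post-injection visits, three time points in the ANOVA, and MAS at the same visits. The plan states no error rate, so there is no figure to reproduce.

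**Assumptions, not in the plan:** two-sided 5% level; correlation between speeds 0.5-0.95, between visits 0.3-0.7 (0.5 or 0.7 in the ANOVA runs), and between torque and MAS 0.2-0.6. MAS is treated as continuous. That is a simplification, because the scale has six ordered grades.

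**Step 1, upper bound if the tests were independent.** The chance of at least one false positive in k tests is 1 - 0.95^k.
- k = 2: 1 - 0.9025 = 9.8%
- k = 4: 1 - 0.8145 = 18.5%
- k = 6: 1 - 0.7351 = 26.5%

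These tests are not independent, because they come from the same patients. Simulation under no effect is therefore needed.

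**Step 2, the planned ANOVA** (repeated-measures form, 40,000 runs for each of 6 settings).

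| What may count | At least one p<0.05 | Multiple of 5% |
|---|---|---|
| GROUP x TIME, one named speed | 4.8-5.2% | 1 |
| GROUP x TIME, either speed | 6.5-9.3% | 1.3-1.9 |
| GROUP x TIME, either speed or MAS | 10-14% | 2.0-2.7 |
| GROUP or GROUP x TIME, one speed | about 10% | about 2 |
| GROUP or GROUP x TIME, either speed | 13-18% | 2.6-3.5 |
| GROUP or GROUP x TIME, either speed or MAS | 20-25% | 3.9-5.1 |

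**Step 3, separate two-group t-tests by visit** (60,000 runs for each of 45 settings).

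| What may count | At least one p<0.05 | Multiple of 5% |
|---|---|---|
| 2 speeds x 2 visits | 11-17% | 2.1-3.5 |
| The same, plus MAS at one visit | 15-21% | 2.9-4.3 |
| The same, plus MAS at both visits | 17-25% | 3.4-5.0 |

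Both tables count findings in either direction. In the last row, false findings favouring the guided arm alone are 8.6-12.9%, against a nominal 2.5% in that direction.

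**Step 4, effect on the future study.** With 14 degrees of freedom the critical t is 2.145. A two-group comparison at 8 per arm is therefore significant only if the observed standardised difference is at least 2.145 x sqrt(2/8) = 1.07. If that minimum is used for planning at 80% power, n per arm = 2 x (1.96 + 0.84)^2 / 1.07^2 = 15.68 / 1.145 = 13.7, or about 14-15 with the t correction. A result picked for significance would thus suggest no more than about 14-15 per arm, whatever the true effect.

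**The case against.** The case for leaving the plan alone has several parts.

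- **One test is planned.** The only named analysis is an ANOVA on reflex torque that takes all three time points in one model. Separate visit-by-visit tests are nowhere planned. If GROUP x TIME decides, the excess error comes from speed alone and is modest (6.5-9.3%). This stands, and it is why no single multiplier can be given. A reader might infer a flat two- to threefold inflation, but the documents support no such figure: they give no level, no correlations and no list of tests that count.
- **MAS is not an equal contender.** It has no planned test and is described as less reliable and open to influence from other muscles. This stands, so the highest figures apply only if MAS tests are added, or (for ANOVA at both speeds) if both effects may count. But the plan still predicts better clinical outcomes, and an informal preference is not a designation.
- **The cited torque method may settle the speed.** Section 4 adopts the measurement protocol of a cited study, which cannot be checked here. If it does settle the matter, the plan needs only to say so.
- **The project is exploratory, with a feasibility purpose.** This also stands. A reader might infer that any one favourable result would be declared proof of superiority. The plan contains no such decision rule. It does predict a significant difference and does intend to size a further study, and for both uses it matters which result was chosen in advance.

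**Conclusion.** The gap is confirmed in the available text: no deciding speed, visit or ANOVA effect is named, and section 6 repeats the open wording of section 4. Under an assumed two-sided 5% level and the correlation ranges shown, the chance of at least one false positive runs from about 6.5-9% (GROUP x TIME at either speed) through about 11-17% (four separate torque comparisons) to about 25% (MAS tests at both visits added, or both ANOVA effects at either speed or on MAS). The multiple of the nominal level is therefore about 1.3 to 5, depending on which tests count. It returns to 1 once a single contrast at one speed is named.

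This limits how a significant result can be read and which effect may size the future study. It is not a breach of a confirmatory claim, because the plan makes none.

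**What to change.** Before outcomes are compared by group, name one primary contrast and its significance level. A suitable choice is the baseline-adjusted group difference in reflex torque at 3 weeks, the time at which the plan itself places the peak effect. Use one pre-named speed. The mean of the two speeds is an alternative only if the sponsor confirms that both are recorded in every patient; the wording that joins the speeds with an or does not establish this. Report the other speed, the 3-month visit, the GROUP x TIME ANOVA and MAS as secondary, with confidence intervals and no superiority claim. State that the future study will be planned from the primary contrast and its interval.

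The cost is wording only: no extra patients, visits or measurements. Power does not argue against the change. With 8 per arm, an assumed 1 SD effect at 3 weeks, 0.5-1 SD at 3 months and visit correlations of 0.3-0.7, power is about 47-70% for the baseline-adjusted contrast, 28-72% for GROUP x TIME and 18-40% for GROUP. The real downside is that an effect seen only at another speed or visit can no longer be the headline.

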- any condition that, in the judgment of a physician, would prevent the person from participating. Efforts will be made to match a variety of measures between two groups, such as age, gender, time from stroke, spasticity in other elbow flexors (e.g., brachioradialis), and injection sites. Given the volume of patients in TIRR Spasticity Management Clinic, we are confident that we can achieve this goal.

Potential subject populations and recruitment: Subjects will be recruited from TIRR outpatient clinic.

6. Data Collection and Analysis

A desktop computer will be used for data acquisition and processing. Data will be saved for off-line analysis using customized MatLab software and Statistica software.

Experiment 1: This is a validation study. Detailed information has been provided above.

Experiment 2: These measures will be made at baseline, 3 weeks and 3 months post-injection. Two-way ANOVA with factors of GROUP (x2) and TIME (x3) will be performed on reflex torque values. It is anticipated that MAS scores, reflex torque values are comparable at baseline, but will be significantly reduced at 3 weeks and 3 months for both groups. Reduction is expected to be significantly more in the IZ-guided injection group than in the standard group. We do anticipate great reduction in elbow flexor spasticity as quantified by reflex-torque measurement after the IZ-guided injection. However, MAS scores are not as reliable in general (Craven and Morris 2010), and could be influenced by other elbow flexors.

Demographic data will be analyzed descriptively. Personal information will be de-identified.

7. Potential Risks/Discomforts:

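### Experiment 2's only stated test, a GROUP by TIME ANOVA on reflex torque, names no patient or within-patient error term although each patient is measured three times, and does not say which effect decides the claim

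*Combined protocol and SAP*

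**What the plan says.** Section 4 (Experiment 2, Treatment outcome evaluation and comparison) sets the visits: "These measures will be made at baseline, 3 weeks and 3 months post-injection". It then gives the analysis: "Two-way ANOVA with factors of GROUP (x2) and TIME (x3) will be performed on reflex torque values". Section 6 (Data Collection and Analysis, Experiment 2) repeats the sentence and adds no error term, covariance structure or software procedure.

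The hypothesis is given in words: "Reduction is expected to be significantly more in the IZ-guided injection group than in the standard group". The opening paragraph of Experiment 2 expects that outcomes "will be better in the 3DIZI-guided injection group than in the standard injection group at 3 weeks and 3 months post-injection", with comparable baselines. It also says: "The clinical effect of BTX injection usually reaches to its peak at about 3 weeks, and lasts for 3 months".

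On numbers of patients: "Eight patients and 16 patients (8 patients per group) are proposed for Exp 1 and Exp 2 respectively". The justification is: "We expect that 8 subjects in each group should be sufficient to detect difference should it exist, according a recent study". On allocation, section 5 says: "Efforts will be made to match a variety of measures between two groups". No randomisation is described.

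**The concern.** Three torque values from one patient are correlated. A two-way ANOVA with only GROUP and TIME has a single residual that mixes between-patient and within-patient variation. That residual is too small for comparing groups overall and too large for comparing changes over time.

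The plan also names no deciding effect. A larger reduction is a question about change, so it points to GROUP by TIME or a change contrast. But the text does not say so, and the GROUP main effect, which averages in a baseline visit where no difference is expected, remains available.

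This is the only inferential test stated for the guided-versus-standard comparison. A wrong error term would distort that result. The power analysis promised at the end of the project could inherit the same error.

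**Working it through.** **The plan's own figure.** The 8 per group cannot be reproduced: no effect size, SD, alpha or power accompanies it.

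**Inputs from the documents.** 2 groups × 8 patients × 3 visits = 48 values.

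**Assumed inputs.** Normal data, unit SD at each visit, alpha 5%, no dropout, equal correlation ρ of 0.5, 0.7 or 0.8, and group differences of (0, 1, 1) SD at the three visits for a sustained benefit.

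**Step 1: expected mean squares with no patient term.**
- Residual (42 df): [14(1+2ρ) + 28(1−ρ)]/42 = 1 at every ρ.
- GROUP under the null: 1+2ρ = 2.0, 2.4, 2.6. The ratio to the residual should be 1, so the test rejects too often.
- GROUP by TIME under the null: 1−ρ = 0.5, 0.3, 0.2. The ratio is below 1, so the test rejects too rarely.

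**Step 2: sustained benefit, no patient term.** The differences (0, 1, 1) deviate from their mean of 2/3 by (−2/3, 1/3, 1/3), with sum of squares 2/3. The interaction sum of squares gains 8 × 2 × (1/4) × (2/3) = 8/3, or 4/3 per df. The expected interaction mean square is therefore 1.83, 1.63 and 1.53, against a critical F(2, 42) of 3.22.

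**Step 3: the same benefit with a patient term.** The interaction is tested on the within-patient error (2, 28 df), with noncentrality (8/3)/(1−ρ) = 5.33, 8.89 and 13.33. Exact power is 48.6%, 71.6% and 88.2%.

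**Step 4: accepting either test with a patient term.** Under equal correlation the two tests are independent, so the null rejection rate is 1 − 0.95² = 9.75%. Simulation gives 9.7–9.8%.

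**Results.** Literal-reading figures are simulated with at least 100,000 trials per scenario; the repeated-measures GROUP power is also simulated.

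| | ρ = 0.5 | ρ = 0.7 | ρ = 0.8 |
|---|---|---|---|
| Literal: GROUP, null rejection | 16% | 21% | 23% |
| Literal: interaction, null rejection | 0.5% | <0.1% | <0.1% |
| Literal: interaction, power at 1 SD | 17% | 12% | 9% |
| Repeated measures: interaction, null rejection | 5% | 5% | 5% |
| Repeated measures: interaction, power at 1 SD | 48.6% | 71.6% | 88.2% |
| Repeated measures: GROUP, power at 1 SD | 33% | 28% | 27% |

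**Sensitivity.**
- At ρ = 0.3 the literal GROUP test rejects 12% under the null, and interaction power is 21% against 36% with a patient term.
- At ρ = 0 there is nothing to correct: the literal tests hold 5%.
- At 1.5 SD the literal interaction has about 50–52% power for ρ of 0.5 to 0.8.
- With unequal correlations, the uncorrected repeated-measures interaction has null size of about 6% (AR(1) 0.7: 5.7%; baseline–post 0.4 with post–post 0.8: 6.5%). A Greenhouse-Geisser correction brings these to 4.6% and 4.9%. Accepting either test gives 10.3% and 11.0%.

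**The case against.** The strongest reply is that repeated measures was meant. The design plainly follows the same patients over three visits, the wording may be shorthand for a mixed-design ANOVA, and the plan says biostatisticians are available. That is plausible, and on that reading the size of the interaction test is nearly right. But neither section says so, and available support is not a stated analysis. The unnamed deciding effect remains under both readings.

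A reader might infer three stronger things, none of which the documents support:

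- *The comparison has a 16–23% false-positive rate.* That needs both the literal reading and a claim of success from the GROUP main effect. The plan leaves this open but does not propose it. The test that fits its stated claim is conservative under the literal reading.
- *Eight per group gives only 9–17% power.* The figure is specific to 1 SD and comes mainly from the missing patient term. The same patients and effect give 48.6–88.2% once the term is in.
- *A 2-df interaction is the wrong test.* A pre-specified interaction is legitimate, and no alternative wins throughout. For a sustained 1 SD benefit, a change contrast on the mean of the two post-injection visits has 57.5%, 79.2% and 92.4% power at ρ of 0.5, 0.7 and 0.8. If benefit is gone by 3 months, it has 19%, 28% and 40%, while the interaction keeps 48.6%, 71.6% and 88.2%.

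It is also fair that Experiment 2 is a feasibility aim in an exploratory project. That lowers the stakes, but the plan still predicts significant differences and calls its sample sufficient to detect one.

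**Conclusion.** The concern holds as an omission that should be fixed. Followed exactly, the stated analysis uses the wrong error term. In the cases examined, the interaction test is far too conservative (null size of 0.5% or less, power of about 9–17% for a sustained 1 SD benefit) and the GROUP test is too liberal (16–23%), the latter mattering only if GROUP is used to claim success. If repeated measures was intended, what remains is modest: about 5% size for the interaction, about 6% uncorrected in the two non-spherical cases, and about 10% error if either GROUP or the interaction may count.

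The sizes rest on assumed alpha, correlation and effect. The direction does not depend on the exact values: for any positive equal correlation, omitting the patient term makes GROUP anti-conservative and the interaction conservative. The documents do not show which reading the investigators will follow, so neither set of figures is a demonstrated property of the trial.

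**What to change.** In sections 4 and 6, replace the ANOVA sentence with one that states:

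1. Reflex torque will be analysed by repeated-measures (split-plot) ANOVA with a sphericity correction, or by a linear mixed model, with patient as the repeated unit.
2. The group difference in change from baseline decides the claim, either as GROUP by TIME or as one change contrast named in advance. The GROUP main effect does not.
3. The estimated group difference in change will be reported with a 95% CI.

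**Optional advice.** The choice among the 2-df interaction, an average over both post-injection visits and 3 weeks alone depends on whether benefit is expected to persist or fade; none is best in every scenario. Change from baseline versus baseline adjustment is also a trade-off, because groups are matched with no randomisation described. With no treatment effect and ρ of 0.5, 0.7 and 0.8, a stable 0.5 SD group offset makes baseline-adjusted ANCOVA reject 9%, 7% and 6%. A 0.5 SD baseline difference that regresses makes the change contrast reject 8%, 7% and 6%. Reporting both, with one named as primary, would be reasonable.

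**Cost.** Text edits only; no new patients, visits or measurements. The Greenhouse-Geisser correction costs roughly 1–8 points of interaction power. The largest loss seen is about 8 points (52.7% to 44.6%), with correlations of 0.4 and 0.8 and benefit gone by 3 months.

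### The one inferential analysis named for Experiment 2, a three-visit GROUP x TIME ANOVA with no missed-visit rule, wastes collected data and power at 8 per group; a mixed model would not

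*Combined protocol and SAP*

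**What the plan says.** Section 4 (Experiment 2, treatment outcome evaluation) and section 6 (Data Collection and Analysis) give the same sentence: "Two-way ANOVA with factors of GROUP (x2) and TIME (x3) will be performed on reflex torque values". The visits are fixed by "These measures will be made at baseline, 3 weeks and 3 months post-injection". The hypothesis concerns change from baseline: "Reduction is expected to be significantly more in the IZ-guided injection group than in the standard group". On timing, the introduction to Experiment 2 says "The clinical effect of BTX injection usually reaches to its peak at about 3 weeks, and lasts for 3 months".

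On numbers, "We plan to recruit 16 post-stroke subjects who are currently receiving BTX injections", and the Limitation paragraph adds "We expect that 8 subjects in each group should be sufficient to detect difference should it exist". No effect size, SD, alpha, power or allowance for losses is given.

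The MAS is also an outcome to be compared, but no test is named for it; demographics are descriptive. The ANOVA is not called repeated-measures. There is no analysis set, missing-data rule, replacement rule or mixed model. The section 5 exclusion list includes a change of antispastic medication during follow-up, which the plan calls clinically rare.

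**The concern.** The named method can be run in two ways, and neither copes with a missed visit.

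- **Repeated-measures ANOVA.** The classical form needs all three values from each patient. One missed 3-month visit also removes that patient's 3-week value, already collected and taken when the effect is expected to be greatest.
- **Plain two-way ANOVA.** Other values are kept, but the three readings from one patient are treated as independent. Stable differences between patients stay in the error term. After a missed visit, the cell means being compared also come from different sets of patients.

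With 8 patients per group, one patient is an eighth of an arm. The plan will use these data to decide whether, and with how many patients, to go further ("A power analysis will be performed at the completion of this project"), so lost precision carries into that decision.

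**Working it through.** **The plan's own figure.** The 8 per group cannot be reproduced, because no inputs are given. Working backwards, a simple two-sided 0.05 comparison of 8 v 8 has 80% power only for a difference of about 1.51 SD (noncentral t).

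**Inputs.** From the documents: 8 per group and three visits. Assumed: two-sided alpha 0.05, SD 1 at each visit, a group difference of 1.2 SD at both follow-ups, within-patient correlation 0.6 (range 0.5 to 0.7), and 5% to 20% of patients missing each follow-up visit.

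**1. How often a patient is incomplete.** With miss rate m at each of two follow-up visits, independently, expected completers are 16(1−m)², and the chance of at least one incomplete patient is 1−(1−m)^32.

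| m | Expected completers | Chance of at least one incomplete |
|---|---|---|
| 5% | 14.4 | 81% |
| 10% | 13.0 | 97% |
| 20% | 10.2 | over 99% |

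**2. Power with complete data, repeated-measures form.** The group differences at the three visits are 0, 1.2 and 1.2, with mean 0.8. The squared deviations sum to 0.64 + 0.16 + 0.16 = 0.96. The noncentrality is λ = [n₁n₂/(n₁+n₂)] × 0.96/(1−ρ).

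- 8 v 8: λ = 4 × 0.96/0.4 = 9.6, F on 2 and 28 df, power 0.75.
- 7 v 7: λ = 3.5 × 0.96/0.4 = 8.4, F on 2 and 24 df, power 0.68.
- 6 v 6: λ = 3 × 0.96/0.4 = 7.2, F on 2 and 20 df, power 0.60.

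At correlation 0.5 or 0.7, the 8 v 8 power is 0.65 or 0.87.

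**3. Power with complete data, plain form.** The interaction mean square is unchanged, but the error mean square now estimates the full variance (1) instead of 1−ρ (0.4). The F ratio is therefore about 0.4 of its proper size. Simulated power is 0.25 to 0.27, against 0.75 in step 2, before any visit is missed.

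**4. Power with visits missed at random** (simulation, correlation 0.6).

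| Missed per follow-up visit | Completer-only ANOVA | REML mixed model, all values |
|---|---|---|
| none | 0.75 | about 0.75 |
| 10% | 0.64 | 0.72 |
| 20% | 0.51 | 0.68 |

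At 10% missed, completer-only power falls from 0.65 to 0.53 at correlation 0.5, and from 0.87 to 0.77 at 0.7.

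**5. Bias in the completers' change from baseline.** True difference 1.00 SD at both follow-ups, 2 of 16 patients missing the 3-month visit, correlation 0.5 to 0.7.

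| Who is lost | 3-week change difference | 3-month change difference |
|---|---|---|
| Two at random | 1.00 | 1.00 |
| Two highest 3-week torques | 0.87 to 0.92 | 1.00 |
| Two poorest 3-week changes | 0.74 to 0.77 | 0.87 to 0.88 |

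**6. Direction.** With a true 3-month difference of −1.20 and loss related to 3-week torque, completers give −1.09 to −1.02 if only poor responders on standard injection leave, and −1.31 to −1.38 if only poor responders in the guided group leave.

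**The case against.** The strongest case against is that the harm depends on losses the documents never quantify. There are only two follow-up visits. Patients already attend this clinic about every three months for injections, so the last assessment falls near a routine return. Section 13 pays the Experiment 2 gift cards after the last visit, which encourages completion. The project calls itself exploratory: "These estimated numbers fit in the scope of work of this 2-year exploratory project". All of this stands, and it is why the power figures are shown over a range of assumed miss rates.

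A reader might infer that poorly controlled patients on standard injection will skip the 3-month visit, so that the benefit of guidance is understated by about a quarter. The documents do not support this. Nothing says who misses visits; poor control could equally be a reason to attend. The difference can also be inflated (step 6). For the raw 3-week torque difference, a shrinkage of about 25% does follow if the two highest 3-week torques are lost with certainty (0.745 instead of 1.00). But the hypothesis concerns reduction from baseline, and there the same losses cost 8% to 13% at 3 weeks and nothing at 3 months. Selection only partly related to outcome gives less. A shrinkage near 25% on change needs loss of the poorest 3-week changes.

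Nor should the mixed model be oversold. In simulations where loss depends only on observed values it is unbiased because its own assumption is met.

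The objection does not reach the plain ANOVA's loss of power, which needs no missed visit, or the discarding of 3-week values by the repeated-measures form whenever a 3-month visit is missed.

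**Conclusion.** The concern holds as one of lost information and precision. Under the assumptions above, dropping incomplete patients costs about 8 points of power relative to a mixed model at 10% missed per visit (0.72 − 0.64) and 17 points at 20% (0.68 − 0.51). Read literally as a plain two-way ANOVA, the plan has roughly a third of the achievable power (0.25 against 0.75) even with full attendance.

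Bias is a possibility only. On change from baseline at 3 weeks, with 2 of 16 lost, it runs from none (random loss), through 8% to 13% (highest torques lost), to about 25% (poorest changes lost). Its direction is undetermined. The effect size, correlation and miss rates are all assumed. The change is worth making because a better method is available at almost no cost. It does not repair the unsupported 8 per group.

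**What to change.** In section 4 (Experiment 2) and section 6, replace the ANOVA sentence with:

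- A REML mixed model for reflex torque with patient as the repeated unit; baseline, 3-week and 3-month values as responses; and group, visit and group-by-visit terms. State the covariance structure (the figures above used compound symmetry).
- Group contrasts in change from baseline at 3 weeks and at 3 months, with Kenward-Roger degrees of freedom.
- Every available value from all injected patients with at least one post-injection value, so that a 3-week value counts whether or not the 3-month visit takes place.
- A statement of how values are analysed for a patient who meets the medication-change exclusion after injection.
- Missed visits and their reasons, reported by group.

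The cost is a change of wording and a standard mixed-model routine; the plan says full-time biostatisticians are available. No extra patients, visits or data are needed. The downside is small: the model relies on missingness being explained by observed values, which is a weaker assumption than the one needed to drop incomplete patients without bias.
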